TITLE: Evaluation of Abdominal Wall Block with Liposomal Bupivacaine for Post-Operative Analgesia in Donor Nephrectomy

NCT#: NCT03294109

DATE: May 20, 2020

Study Title:

“Evaluation of Abdominal Wall Block with Liposomal Bupivacaine for Post-Operative Analgesia in Donor Nephrectomy”

List of Abbreviations:

TAP block: Transverse abdominis plane block

TQL block: Transmuscular quadratus lumborum block

LA: Local Anesthetic

Principal Investigator, Research Team, and Study Site:

Principal investigators: [name] MD, [name] MD

Co-Investigators: [name] MD, [name] MD, [name] MD, [name] MD, [name], [name], [name]

Research team and contact information:

UCLA Department of Anesthesiology
and Perioperative Medicine

Ronald Reagan UCLA Medical Center

[name]

[name]

[contact]

University of California, Los Angeles

Department of Urology

David Geffen School of Medicine at UCLA

[name]

[name]

[name]

[contact]

Study site: UCLA Medical Center, Ronald Reagan Hospital

Background and study population

The study population will include patients greater than 18 years of age undergoing laparoscopic donor nephrectomy surgery.

Study Design

Randomized blinded controlled clinical trial

Sample Size

50 each arm. 100 total.

Study Duration

18-24 months.

Primary Objective

To determine the degree of pain control in patients receiving a long acting TQL block in addition to a short half-life TAP block compared to TAP block alone (i.e., the current standard of care) after laparoscopic donor nephrectomy. This outcome will be measured using pain scores on a numeric scale obtained during standard inpatient care as well as via the APS-POQR and PROMIS-29, two standard, validated questionnaires.

Secondary Objectives

- To determine patient satisfaction as measured by a satisfaction item at post-operative days 1 and 90.
- To measure changes in quality of life via the PROMIS-29, bowel function via the Bowel Habits Questionnaire (BHQ), male (International Index of Sexual Function; IISF) and female sexual function (Female Sexual Function Index; FSFI) across time and in the study group (patients receiving liposomal bupivacaine TQL block in addition to TAP block) as compared to our conventional post-operative pain management. See attached questionnaire schedule for timing of these items.

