Those patients who agree to participate and provide written consent will be enrolled into the study and instructed in the electronic completion of study questionnaires using the Urology Patient Data Waystation (UPDW). Unique, personalized log-in information will be sent to the patient either by email or using the secure MyChart messaging system, based on patient preference, to access UPDW for each time point. Initial questionnaires at enrollment will collect baseline quality of life, bowel and sexual function, and demographic data. When the surgery date has been determined, patients will receive a message to complete a second set of baseline survey questionnaires using the same system if their surgery date is more than 6 months past the date of completion of their initial baseline survey. Those participants who completed their initial baseline within 6 months of their surgery date will only complete one baseline survey.

When surgery is scheduled, each enrolled patient will be randomized (alternating, blocked randomization) to either the study group to receive liposomal bupivacaine TQL block in addition to standard of care post-operative pain management or to the control group to receive our current standard of care. Randomization will maintain equal numbers of participants in each group by sex due to the increased risk of post anesthesia nausea in females.

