Preliminary power analysis was performed as noted in table 1 below. We believe that utilization of this novel block can produce a pain score reduction of approximately 40% compared to current standard practice. Assuming a study power of 80% and pain score reduction of 40%, we need to enroll approximately 17-20 patients per study arm. However, to demonstrate a clear clinically significant difference we need to enroll over 37 patients per arm. Since some patients may not complete the study, we feel that 50 patients per group will provide sufficient sample size

to determine the benefit versus cost of the study procedure. This is similar to the samples sizes used in the literature.

Pain scores, nausea scores, and total opiate consumption for 24 hours will be analyzed using a T-test of means. Satisfaction will be assessed using a T-test.

Table 1. Power Analysis

Mean 1	Mean 2	Std.	Reduction	Power	n per group
8	4	1	50%	80%	3
7.5	4.5	1	40%	80%	4
7	5	1	29%	80%	6
8	4	2	50%	80%	6
7.5	4.5	2	40%	80%	9
7	5	2	29%	80%	17
8	4	3	50%	80%	10
7.5	4.5	3	40%	80%	17
7	5	3	29%	80%	37

Additional Data Use:

We are interested in using the data collected with this protocol in connection with the CURES Database to analyze the data and investigate whether participants use narcotics prior to donor nephrectomy.

The following will be collected:

1. Historic use of narcotic medication will be collected using the CURES Database (<https://oag.ca.gov/cures>). Patients will be cross-referenced from this study database to the CURES search by name and date of birth. The data points we are searching for are for any narcotic prescription 12 months prior to donor nephrectomy. Also, the date of narcotic prescription closest to date of donor nephrectomy.
2. The milligram morphine equivalent of narcotic medication provided on discharge:
 - a. We will get this information from UCLA CareConnect, and cross-referenced with CURES database.
3. Long-term use of narcotic medication will be collected through the CURES Database. We are collecting to see if they have any narcotic prescriptions in the 0-12 month period after donor nephrectomy excluding discharge prescription. Finally we are finding the furthest narcotic prescription in the 0-12 month period after donor nephrectomy excluding the discharge prescription.

Informed Consent Process:

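### Baseline PROMIS-29, bowel and sexual-function scores are collected for a between-arm comparison of changes, but the Statistical Analysis Plan never uses them and names only unadjusted t-tests

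*Combined protocol and SAP*

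**What the plan says.** All references are to the combined protocol and SAP.

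- **Baseline is measured.** Study design/methodology: "Initial questionnaires at enrollment will collect baseline quality of life, bowel and sexual function, and demographic data". A second baseline set is requested "if their surgery date is more than 6 months past the date of completion of their initial baseline survey", so some patients will have two.
- **The scores are to be compared as changes.** Secondary Objectives: "To measure changes in quality of life via the PROMIS-29, bowel function via the Bowel Habits Questionnaire (BHQ"), together with IISF in men and FSFI in women, over time and against conventional management.
- **PROMIS-29 also serves the primary objective.** The Primary Objective measures pain by a numeric score "as well as via the APS-POQR and PROMIS-29, two standard, validated questionnaires".
- **Analysis methods.** The Statistical Analysis Plan has two sentences on method: "Pain scores, nausea scores, and total opiate consumption for 24 hours will be analyzed using a T-test of means" and "Satisfaction will be assessed using a T-test". There is no covariate, adjusted model or repeated-measures model, and no rule for which baseline to use.
- **Follow-up.** Post-discharge surveys are sent on days 3, 5, 10, 30 and 90, and patients may decline any question (Study design/methodology).

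**The concern.** The trial gathers a pre-surgery value for each of these instruments, and its objectives require a between-arm comparison of them, yet no analysis connects the two. An analyst who carries the plan's only named tool over to these scores must either ignore the baseline or test change scores.

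The first course gives up precision already paid for and leaves any chance baseline imbalance in the estimate. The second can be less precise than ignoring the baseline altogether. If neither is written down, the choice can be made after the data are seen.

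Separate tests at each day also discard patients who skipped that survey, even when their other responses are available. Sexual function is the most exposed outcome: the Objectives section says it has not been closely studied after donation, and each sex-specific instrument uses only part of each arm.

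**Working it through.** **1. The plan's own figure.** The Statistical Analysis Plan introduces its calculation with "Preliminary power analysis was performed as noted in table 1 below". The last row of Table 1 has means 7 and 5, SD 3, 80% power and 37 per group. The significance level is not stated; two-sided 5% is assumed. The standardised difference is (7 − 5)/3 = 0.667. Noncentral-t power is 80.8% at 37 per group and 79.7% at 36, so 37 is reproduced. The other eight rows reproduce in the same way. The table concerns pain scores and takes no account of a baseline, so this point leaves it as it is.

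**2. Inputs for the comparison.**
- Patients: 50 per arm (Sample Size). This is an upper limit, because the plan expects some patients not to complete.
- Test: two-sided 5% (assumed, as above).
- Correlation r between baseline and follow-up: not in the documents; taken as 0.3, 0.5 and 0.6.
- Equal SDs at baseline and follow-up (assumed).

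**3. Variance of the arm difference, relative to a t-test of follow-up scores alone (= 1).**
- Change score: 2(1 − r)
- ANCOVA: 1 − r²

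The change score is noisier than follow-up alone when 2(1 − r) > 1, that is, only when r < 0.5. ANCOVA never exceeds 1. It never exceeds the change score either, because 2(1 − r) − (1 − r²) = (1 − r)² ≥ 0. The only cost is one degree of freedom.

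**4. Power.** With 50 per arm, the unadjusted t-test has 80% power at 0.566 SD. The other powers come from the noncentral t at 0.566 divided by the square root of the variance factor. For example, at r = 0.5 ANCOVA has 0.566/√0.75 = 0.653.

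| r | Change-score variance | ANCOVA variance | Power, follow-up only | Power, change score | Power, ANCOVA | ANCOVA gain in effective patients (1/(1 − r²) − 1) |
|---|---|---|---|---|---|---|
| 0.3 | 1.40 | 0.91 | 80% | 66% | 84% | 10% |
| 0.5 | 1.00 | 0.75 | 80% | 80% | 90% | 33% |
| 0.6 | 0.80 | 0.64 | 80% | 88% | 94% | 56% |

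**5. Sexual function.** IISF applies to men and FSFI to women, so the table's powers do not describe them. If the sexes were equal in number (an assumption), each would have about 25 per arm. The unadjusted t-test would then have 50% power at 0.566 SD, and would need 0.81 SD for 80%. The variance factors in step 3 hold at any sample size.

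**The case against.** The strongest reply is that the plan does not prescribe an unadjusted t-test for these questionnaires. Its t-tests are assigned to pain scores, nausea scores, 24-hour opiate consumption and satisfaction, and those outcomes have no matching baseline in the plan, except possibly the PROMIS-29 pain items. This is correct. For PROMIS-29 quality of life, BHQ, IISF and FSFI the defect is an omission.

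Three stronger readings are tempting, and the documents support none of them.

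- A reader might infer that change scores will be t-tested. The word appears only in the objective; no analysis of change is specified.
- A reader might infer that the correlation is likely to be below 0.5, because healthy donors are compared with their state soon after surgery. The documents give no correlation, and follow-up runs to day 90. At r = 0.6 a change-score test would beat the raw t-test, 88% against 80%.
- A reader might infer that the primary t-test covers PROMIS-29 pain items. The Primary Objective lists the numeric score separately from PROMIS-29, and the Objectives section describes scores recorded by nursing staff on a visual analog scale. That the t-test extends to the PROMIS-29 items is possible but not stated.

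It is also fair to say that ANCOVA at each day does not solve the skipped-survey problem, and that sex cannot be a covariate within a single-sex instrument. Both limits are met in the remedy. None of this removes the gap: baseline data are collected, a comparison is promised, and no use of the baseline is planned.

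**Conclusion.** The point holds as an omission with a clear remedy. The plan gives no baseline-adjusted analysis for PROMIS-29, BHQ, IISF or FSFI, and the only methods it names would use the baseline badly or not at all if carried over to these scores.

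For PROMIS-29 and BHQ, adjustment cuts variance by 9%, 25% or 36% at r = 0.3, 0.5 or 0.6. That is a gain of 4, 10 or 14 percentage points of power at 0.566 SD with the full 50 per arm. These sizes rest on the assumed correlations, equal SDs and a two-sided 5% test. A baseline may be up to six months old at surgery, which could lower r, but the documents do not allow this to be quantified. The recommendation does not depend on r.

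The point concerns mainly secondary outcomes, plus the PROMIS-29 component of the primary objective. It should be corrected, but it does not threaten the sample size.

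**What to change.** Add to the Statistical Analysis Plan, for PROMIS-29 (including its pain scores), BHQ, IISF and FSFI:

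- Compare arms with a baseline-adjusted model: either ANCOVA at each day, or one mixed model for repeated measures over the days on which the instrument is given, with arm, day and arm-by-day terms. Prefer the mixed model where skipped surveys are a concern, because it keeps patients who answer on some days only.
- Use the last pre-surgery score as the covariate, that is, the later one where two exist.
- Include sex, the randomization factor, for PROMIS-29 and BHQ only. Analyse IISF within men and FSFI within women, with no sex term.
- Report the adjusted arm difference with a 95% confidence interval at each day.
- State that unadjusted t-tests of follow-up or change scores will not be used for these instruments.

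The cost is a few lines of text. No new data, visits or patients are needed.

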The following study variables will be collected postoperatively following arrival in the post-anesthesia care unit: Current and maximum intensity pain scores will be documented by nurses in the electronic medical record (EMR). Total opiate dose consumed every 24 hours will be collected from EMR and electronic survey after discharge. Patient satisfaction will be evaluated using the Revised American Pain Society Patient Outcome Questionnaire (APS-POQ-R) provided on post-operative day 1 by a research assistant or study coordinator. The incidence of nausea or vomiting will be extracted from nursing notes and queried via electronic surveys. Post-discharge, which is typically 1-2 days following surgery, patients will be sent surveys delivered by the UPDW database server 3, 5, 10, 30, and 90 days post-surgery. If patients do not respond 90 days post-surgery study team will contact patients to attempt to have the exit survey completed.

Complications will be documented in the EMR by the anesthesia pain service, urology service, and nurses who will monitor these patients while admitted. Urology and study staff will follow the patients following discharge, including a post-operative office follow-up approximately 1 week post-surgery, as is standard of care

Study Population:

Patients at least 18 years of age undergoing laparoscopic donor nephrectomy. Pregnant patients will be excluded. Patients with local infection at the potential block site or any contraindication to kidney donation, local, or general anesthesia will be excluded.

Study Duration/Study Timeline:

We anticipate a high level of enrollment since most patients have previously consented to having a block placed and pain minimization is generally a high priority. Given the current volume of donor nephrectomies we expect enrollment to be complete within one year. The duration of the study will depend on the timing from consent for surgery until the operation is scheduled. In most cases this occurs within 2-3 months. The study data collections will conclude 90 days after surgery unless the patient was not able to complete the survey. Additional attempt to contact the patient after 90 days post-surgery may be enacted to have the patient(s) complete an exit survey. See the attached study time line in Appendix A.

Statistical Analysis Plan:

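### Prior 12-month narcotic prescription is collected but left out of the pain and opioid comparisons, and later prescriptions are not split into new and continuing use

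*Combined protocol and SAP*

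**What the plan says.** Eligibility is set out under Study Population: "Patients at least 18 years of age undergoing laparoscopic donor nephrectomy. Pregnant patients will be excluded". The remaining exclusions are these: "Patients with local infection at the potential block site or any contraindication to kidney donation, local, or general anesthesia will be excluded". Opioid use before surgery is not mentioned in either sentence.

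Under Study design/methodology the only balancing factor is sex: "Randomization will maintain equal numbers of participants in each group by sex due to the increased risk of post anesthesia nausea in females".

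The Statistical Analysis Plan says: "Pain scores, nausea scores, and total opiate consumption for 24 hours will be analyzed using a T-test of means". Satisfaction is also compared by t-test. No covariate, stratum, subgroup or sensitivity analysis is named.

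The Additional Data Use section adds prescription-database data, in order to "investigate whether participants use narcotics prior to donor nephrectomy". Item 1 covers the period before surgery: "The data points we are searching for are for any narcotic prescription 12 months prior to donor nephrectomy". It also records the date of the prescription closest to surgery. Item 3, labelled as long-term use, covers the period after: "We are collecting to see if they have any narcotic prescriptions in the 0-12 month period after donor nephrectomy excluding discharge prescription". It also records the furthest prescription within that year. The section states no analysis that links items 1 and 3.

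**The concern.** Lower narcotic requirement is a secondary objective, and the Background makes a clinically significant opioid-sparing effect part of the case for the drug's cost. Earlier narcotic use plausibly predicts both postoperative opioid dose and pain. A baseline variable of that kind, already collected, would normally be used to sharpen the treatment comparison. With 50 donors per arm, a handful more prior users in one arm would shift the observed difference, and the planned test makes no correction for it. If adjustment is not prespecified, any later decision to adjust would also be made with the data in view.

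The field for the year after donation raises a different issue. A donor with prescriptions both before and after surgery is recorded in the same way as one whose first prescription came after surgery. A single summary percentage would therefore mix continued use with new use.

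**Working it through.** **The plan's own figure.** Table 1, last row: means 7 and 5, SD 3, 80% power, 37 per group. A two-sample t-test calculation (noncentral t, two-sided 0.05, which the plan does not state and is assumed here) gives 37, and it matches all nine rows of the table. The sample size is not in dispute. At 50 per arm the power for this scenario is 0.910 (t) or 0.915 (normal approximation).

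**Assumed inputs.** The documents give neither the prevalence of prior use, p, nor its effect on the outcome, d (in within-group SD). Take p = 5-20% and d = 1.

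**Share of outcome variance explained.** R² = p(1−p)d² / (1 + p(1−p)d²).

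**Power at 50 per arm for 7 vs 5 (normal approximation).** This depends on what Table 1's SD of 3 represents, which the plan does not say.
- Reading A: 3 is the ordinary SD, with prior-use variation included. Unadjusted power is 0.915, and adjusted power is Φ(3.333/√(1−R²) − 1.96), where 3.333 = 2/(3 × √(2/50)).
- Reading B: 3 excludes prior-use variation. The unadjusted SD is then 3√(1 + p(1−p)d²), and unadjusted power falls below 0.915.

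| p | R² | A: adjusted power (unadjusted 0.915) | B: unadjusted power (adjusted 0.915) |
|---|---|---|---|
| 5% | 0.0475/1.0475 = 4.5% | 0.927 | 0.903 |
| 10% | 0.09/1.09 = 8.3% | 0.936 | 0.891 |
| 20% | 0.16/1.16 = 13.8% | 0.948 | 0.872 |

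**Chance imbalance.** At p = 10% the SD of the between-arm difference in proportions is √(2 × 0.09/50) = 0.06. A split of 8 versus 2 prior users is a difference of 6/50 = 0.12, or 2 SD. With independent binomial counts, the probability that the arms differ by 5 or more prior users is 0.04, 0.13 and 0.26 at p = 5%, 10% and 20%.

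**Effect of that split on the estimate.** 0.12 × 1 SD = 0.12 SD. The standard error at p = 10% is √(1.09) × √(2/50) = 0.21 SD, so the shift is 0.12/0.21, about 0.6 standard errors. On a pain scale with SD 3 it is 0.12 × 3 = 0.36 points, against planned differences of 2 points (7 vs 5) and 3 points (7.5 vs 4.5). The plan gives no planning effect for opioid use, so the same comparison cannot be made there.

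**Pooling in the 0-12 month field.** Let a be the proportion of prior users, and b the proportion of other donors, with a later prescription. The pre-existing share of all those with a later prescription is pa / (pa + (1−p)b).
- Lowest over the assumed ranges (p = 5%, a = 50%, b = 10%): 0.025/(0.025 + 0.095) = 21%.
- Highest (p = 20%, a = 80%, b = 5%): 0.16/(0.16 + 0.04) = 80%.
- Single illustration: of 100 donors, 10 are prior users and 5 of them continue, while 5 of the other 90 start. Then 5 of 10, or half, were users beforehand.

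**The case against.** An unadjusted t-test in a randomized trial is a valid analysis. Omitting a baseline covariate does not bias the arm comparison, and the test's standard error already allows for chance imbalance. The 2-SD split above moves the estimate by only about 0.6 standard errors, and power for pain is above 0.9 before any adjustment if the SD of 3 is the ordinary one. All of this stands. It limits the point to precision and to prespecification.

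Donors are described as carefully screened, so prior use may be rare and the gain slight. That also stands. A reader might infer from the data collection that the sponsor expects prior users, but the stated purpose is to find out whether there are any. The documents give no prevalence.

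A reader might also infer that the trial defines a long-term-use endpoint that cannot show whether the block prevents persistent use. The text does not support this. Item 3 is in a list of data to be collected, no objective claims prevention of persistent use, and the opioid objective runs to 90 days. Prior and later prescriptions are held for the same participants, so new and continuing use can be separated at analysis. What remains is that the plan does not say they will be.

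Finally, any prescription within 12 months is not the same as current use: one short course 11 months earlier would count. This is a fair criticism of a bare yes/no covariate, and it is why recency belongs in a sensitivity analysis.

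**Conclusion.** The point holds as an improvement in efficiency and reporting. A baseline variable that the trial already collects is absent from the comparisons it could sharpen. On assumed inputs of 5-20% prior users and a 1 SD shift, it accounts for about 4.5-14% of outcome variance. For the 7 vs 5 pain scenario that is worth roughly 1 to 4 percentage points of power at 50 per arm, whichever way Table 1's SD is read. The effect is probably modest, and it would be close to nil if prior use is rare. It would be wrong to conclude that the planned t-tests are biased or invalid, or that the sample size is inadequate.

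The 0-12 month field would pool continuing with new users only if it were summarized as collected. The share of pre-existing users could then be anywhere from 21% to 80% under the assumed ranges, so the split should be stated in advance.

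**What to change.** In the Statistical Analysis Plan, replace the t-tests for opioid use and pain with a linear model containing treatment arm and prior 12-month narcotic prescription (yes/no). Add a sensitivity analysis that replaces yes/no with recency, taken from the collected date of the prescription closest to surgery. Tabulate prior use by arm.

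In Additional Data Use, state that prescriptions 0-12 months after donation, other than the discharge prescription, will be reported separately for donors with and without a prior prescription, and that only those in donors without one will be called new use.

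The cost is a few lines of wording and one extra model term. No new data are needed, and eligibility, randomization and sample size do not change.
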